2 PROTOCOL SUMMARY

2.1 Study objectives

2.1.1 Primary objective

To demonstrate the clinical efficacy of rozanolixizumab in patients with generalized myasthenia gravis (MG).

2.1.2 Secondary objective

To assess safety and tolerability of rozanolixizumab in MG patients.

2.1.3 Other objectives

- To assess pharmacokinetic (PK) characteristics of rozanolixizumab
- To assess the pharmacodynamics (PD) effects of rozanolixizumab on IgG, disease-specific autoantibodies
- To evaluate the emergence and incidence of anti-drug antibody (ADA) and impact on PK and PD
- To evaluate the effects of rozanolixizumab on the concentration of total protein, IgM, IgA, and IgE, serum and plasma complement levels and serum cytokines
- To assess the effect of rozanolixizumab on tetanus IgG antibodies
- To assess the effect of rozanolixizumab on exploratory biomarkers and protein expression, and explore the relationship between protein, and metabolite biomarkers and cause, progression, and appropriate treatment of MG

2.2 Study endpoints

2.2.1 Efficacy endpoints

2.2.1.1 Primary efficacy endpoint

- Change from Baseline to Day 43 (Visit 10) in MG-activities of daily living (ADL) score

2.2.1.2 Secondary efficacy endpoints

- MG-ADL responder (≥ 2.0 points improvement from Baseline) at Day 43 (Visit 10)
- Change from Baseline to Day 43 (Visit 10) in MG-Composite (MG-C) score
- Change from Baseline to Day 43 (Visit 10) in quantitative myasthenia gravis (QMG) score
- Change from Baseline to Day 43 (Visit 10) in the MG Symptoms patient-reported outcome (PRO) 'Muscle Weakness Fatigability' score
- Change from Baseline to Day 43 (Visit 10) in the MG Symptoms PRO 'Physical Fatigue' score
- Change from Baseline to Day 43 (Visit 10) in the MG Symptoms PRO 'Bulbar Symptoms' score

2.2.1.3 Other efficacy endpoints

- Use of rescue therapy due to worsening (IVIg, PEX)
- Time to first rescue therapy
- Time to MG-ADL response (≥ 2.0 points improvement from Baseline)
- Change from Baseline in QMG at each scheduled assessment during Treatment and Observation Periods
- QMG responder (≥ 3.0 points improvement from Baseline) at each scheduled assessment during Treatment and Observation Periods
- Change from Baseline in MG-C score at each scheduled assessment during Treatment and Observation Periods
- MG-C responder (≥ 3.0 points improvement from Baseline) at each scheduled assessment during Treatment and Observation Periods
- MG-ADL responder (≥ 2.0 points improvement from Baseline) at each scheduled assessment during Treatment and Observation Periods
- Change from Baseline in the MG Symptoms PRO 'Muscle Weakness Fatigability' score at each scheduled assessment during Treatment and Observation Periods
- Change from Baseline in the MG Symptoms PRO 'Physical Fatigue' score at each scheduled assessment during Treatment and Observation Periods
- Change from Baseline in the MG Symptoms PRO 'Bulbar Symptoms' score at each scheduled assessment during Treatment and Observation Periods
- Change from Baseline in the MG Symptoms PRO 'Respiratory Symptoms' score at each scheduled assessment during Treatment and Observation Periods
- Change from Baseline in the MG Symptoms PRO 'Ocular Symptoms' score at each scheduled assessment during Treatment and Observation Periods
- Patient Global Impressions of Severity (PGI-S) at each scheduled assessment during the Treatment and Observation Periods

- Patient Global Impressions of Change (PGI-C) at each scheduled assessment during Treatment and Observation Periods
- Change from Baseline in MG-ADL (excluding ocular items) at each scheduled assessment during Treatment and Observation Periods
- Change from Baseline in QMG (excluding ocular items) at each scheduled assessment during Treatment and Observation Periods
- Change from Baseline in MG-C score (excluding ocular items) at each scheduled assessment during Treatment and Observation Periods
- Change from Baseline to Day 43 in MG Quality of Life 15 Item scale revised (MG-QOL15r)
- Change from Baseline to Day 43 in Euro-Quality of Life 5-Dimensions, 5 levels (EQ-5D-5L)
- Minimal Symptom Expression (MG-ADL score of 0 or 1) at any time up to and including Day 43 (Visit 10)
- Change from Baseline in MG Impairment Index (MGII) scores at each scheduled assessment during Treatment Period
- Change from Baseline in MGII ocular sub-scores at each scheduled assessment during Treatment Period
- Change from Baseline in MGII generalized domain sub-scores at each scheduled assessment during Treatment Period

2.2.2 Pharmacokinetic/pharmacodynamic endpoints

2.2.2.1 Pharmacokinetic endpoint

- Plasma concentration of rozanolixizumab at each scheduled assessment during the Treatment and Observation Periods.

2.2.2.2 Pharmacodynamic endpoints

- Change (absolute and percentage) from Baseline in MG-specific autoantibodies at each scheduled assessment during the Treatment and Observation Periods
- Change (absolute and percentage) from Baseline in serum total IgG and IgG subclasses concentrations at each scheduled assessment during the Treatment and Observation Periods

2.2.3 Safety endpoints

2.2.3.1 Secondary safety endpoints

- Occurrence of treatment-emergent adverse events (TEAEs)
- TEAEs leading to withdrawal of investigational medicinal product (IMP)

2.2.3.2 Other safety endpoints

- Occurrence of adverse events of special monitoring (AESM)
- Vital sign changes from Baseline (systolic and diastolic blood pressure (BP) and pulse rate at each scheduled assessment during the Treatment and Observation Periods)

- 12-lead electrocardiogram (ECG) change from Baseline at each scheduled assessment during the Treatment and Observation Periods
- Laboratory change from Baseline at each scheduled assessment during the Treatment and Observation Periods (hematology, clinical chemistry, and urinalysis)
- Suicidality as measured by the Columbia Suicide Severity Rating Scale (C-SSRS)

2.2.4 Anti-drug antibody endpoints

- ADA status at each scheduled assessment during the Treatment and Observation Periods

2.2.5 Immunological endpoints

- Change from Baseline in serum complement levels (C3 and C4) and plasma complement levels (C3a and C5a) at each scheduled assessment during the Treatment and Observation Periods
- Change from Baseline in serum cytokines at each scheduled assessment during the Treatment Period
- Change from Baseline in serum immunoglobulin concentrations (total IgA, IgE, and IgM) at each scheduled assessment during the Treatment and Observation Periods
- Change from Baseline in anti-tetanus toxoid serum titers at each scheduled assessment during Treatment and Observation Period

2.2.6 Other and exploratory endpoints

- Exploratory biomarkers may be measured to evaluate the effect of rozanolixizumab
- Proteins, and metabolites changes that may be measured to understand the cause, progression, and appropriate treatment of MG

A specific SAP will be written to describe the analysis methods for those endpoints, as the results will not be summarized in the CSR. The nature and format of these analyses will be detailed in this SAP.

2.3 Study design and conduct

This is a Phase 3, multicenter, randomized, double-blind, placebo-controlled, 3-arm, repeat dose study evaluating the efficacy and safety of two doses of rozanolixizumab and matching placebo in patients with generalized MG who experience moderate to severe symptoms (Myasthenia Gravis Foundation of America [MGFA II-IVa]) and are being considered for additional treatment such as IVIg or PEX.

Fixed unit doses across body weight tiers and study arms will be employed:

Treatment Arm 1 (rozanolixizumab) – equivalent to approximately [REDACTED]

- Bodyweight <50kg: dose to be administered [REDACTED]
- Bodyweight ≥50kg and <70kg: dose to be administered [REDACTED]
- Bodyweight ≥70kg and <100kg: dose to be administered [REDACTED]
- Bodyweight ≥100kg; dose to be administered [REDACTED]

Treatment Arm 2 (rozanolixizumab) – equivalent to approximately [REDACTED]

- Bodyweight <50kg: dose to be administered [REDACTED]
- Bodyweight \geq 50kg and <70kg: dose to be administered [REDACTED]
- Bodyweight \geq 70kg and <100kg: dose to be administered [REDACTED]
- Bodyweight \geq 100kg; dose to be administered [REDACTED]

The placebo arm will be 0.9% sodium chloride aqueous solution (physiological saline, preservative free) for subcutaneous (sc) administration.

Approximately up to 388 study participants will be screened at about 135 sites from North America, Europe and Asia to achieve the minimum targeted number of 150 to a maximum of 240 evaluable study participants.

Participants have the opportunity to rollover into an open-label extension (OLE) study, as described below. The OLE study, MG0004 ([REDACTED] chronic treatment) will be replaced by MG0007, which consists of [REDACTED] based on MG worsening. Upon study site approval of MG0007, as well as fulfilment of regulatory requirements, study participants will have the opportunity to rollover directly into MG0007. In the event a study participant has already started MG0004, a minimum treatment duration of 6 visits (if IMP treatment is held for low IgG, study participants missed dose(s) can be counted as part of the total 6 visits for completion of MG0004 and meet eligibility requirements for MG0007) must be completed prior to moving into MG0007. Once the site is active for MG0007, no further participants will enroll in MG0004 and the study will be closed at the site once all eligible study participants have discontinued MG0004 and had the opportunity to rollover into MG0007.

The maximum duration of MG0003 study per study participants will be up to 18 weeks, consisting of a Screening Period (1 to 28 days to account for central laboratory turn-around time), a Treatment Period (6 weeks), and a blinded Observation Period (8 weeks).

[figure not shown]
1. All study participants who complete the 6-week Treatment Period may roll over into an 8-week Observation Period.
2. All eligible study participants who complete the Observation Period will be invited to be re-randomized into an OLE study to either active dose arm 1 or 2.
3. Study participants who experience disease worsening during the 6-week Treatment Period (e.g., an increase of 2 points on the MG-ADL or 3 points on the QMG scale between two consecutive visits) may be considered for rescue therapy (IVIg or PEX) at the discretion of the Investigator.
4. Study participants who need rescue therapy during the 6-week Treatment Period will receive IVIg or PEX and complete any subsequent visit(s). No further infusions of rozanolixizumab will be administered after initiation of rescue therapy. Once the participant completes Visit 10, he or she will move into the 8-week Observation Period.
5. Study participants who complete the Treatment Period and require initiation of rescue therapy after they start the 8-week Observation Period, may either opt to receive IVIg or PEX or complete the EOS visit and immediately roll over into an OLE study where the participant

will receive rozanolixizumab. Participants who opt to receive IVIg or PEX will complete any remaining visits in the Observation Period and will not be invited to join an OLE study.

6. Study participants who did not complete the 6-week Treatment Period because they needed rescue therapy and require initiation of a second course of rescue therapy while in the 8-week Observation Period can roll over to an OLE study if a minimum of 2 weeks have lapsed since completion of the last IVIg or PEX session. The EOS visit must be completed before enrolling into an OLE study. Alternatively, they can be treated with IVIg or PEX. Study participants who opt to receive IVIg or PEX will complete any remaining visits in the Observation Period and will not be invited to join an OLE study.
7. Study participants who discontinue study medication for any reason other than requiring rescue therapy will not be eligible for enrollment into an OLE study.

A schematic diagram of the study is provided in [Figure 2-1](#).

FIGURE 2-1: STUDY SCHEMATIC

IVIg=intravenous immunoglobulin G; PEX=plasma exchange; Rozimab=rozanolixizumab

2.4 Determination of sample size

As detailed in [Section 4.4](#), this study will consist of 2 stages, with a formal interim analysis at the end of Stage 1.

Based on historical data, the mean difference in adjusted changes from Baseline of MG-ADL at Day 43, between rozanolixizumab and placebo, is assumed to be 1.5 to 2.0 and the standard deviation is assumed to be 3.5 to 4. A difference of >1.5 could be judged to be clinically meaningful.

It is proposed that the interim analysis will be conducted when approximately 90 eligible study participants have been treated and are evaluable for the primary endpoint, i.e., approximately 30 study participants per dose group in Stage 1. If the study is not stopped for futility after Stage 1, the sample size will be increased, subject to a maximum cap, to provide an overall conditional power target of 90% based on the observed effect size in Stage 1. For each dose that is not futile, the comparison-wise conditional power will be calculated which is the probability of, given the observed data, to achieve a significant result for the completed trial if only the considered treatment is selected. If two doses are selected, then the conditional power associated with the higher treatment effect will be used to determine the stage 2 sample size. Conditional power will be calculated as described in formula 7.2 of Wassmer and Brannath (2016). Similarly, the stage 2 sample size required to achieve a target conditional power of 90% will be calculated using a formula derived from formula 7.4 of Wassmer and Brannath (2016) as follows:

$$\text{Second stage sample size per arm} = 2 * SD^2 * [\phi^{-1}(TP) + \phi^{-1}(1-CRP)]^2 / \Delta^2$$

Where,

SD = pooled standard deviation from the stage 1 statistical model using all dose groups

TP = target conditional power = 0.9

CRP = Conditional rejection probability at stage 1 for the dose group being considered

Delta = assumed true treatment effect for second stage data

If two doses are considered for stage 2 then the above formula will be applied with the conditional error divided by two, to account for multiplicity. Depending upon the selection of one, or two, of the doses after Stage 1, a further 60 to up to a maximum of 150 eligible study participants will be randomized in Stage 2 of the study. Thus, the total sample size of the study could range between 150 and 240 study participants if the study is not futile at Stage 1.

The power of the study using the above adaptive design and expected sample sizes with a sample size cap of 80 per arm and various scenarios of true treatment effect and standard deviation were determined from a stimulation study using the statistical software ADDPLAN MC, the results of which are summarized in [Table 2-1](#).

The simulation results also indicate that across the various scenarios the average sample size for the study ranges between 169 and 203 study participants. The power for scenarios 5 to 7 and 12 to 14, that is, when the high dose has an effect compared to placebo of 2 points, are at least 80%, indicating that the sample size re-assessment process helps maintain reasonable power when only one dose has a clinically meaningful effect of 2 and the data variability is greater than anticipated (standard deviation[SD]=4).

The chances of stopping the study for futility i.e. both doses individually futile, when at least one dose has a clinically meaningful true effect of 2 or more versus placebo, is less than 3%.

These results support the strategy of entering 30 eligible study participants per dose group in Stage 1 and between 30 to 50 study participants per dose group in Stage 2. Note that ADDPLAN MC implements the sample size increase rule 'per arm' rather than 'per stage', so that if only one dose is selected for Stage 2, then the maximum sample size for this stage is 100, whereas if two

doses are selected than the maximum Stage 2 sample size is 150. Therefore, if an overall study sample size cap of 240 (i.e., 150 in Stage 2) were implemented, irrespective of whether one or two doses are selected, then we would expect power for each scenario to be slightly increased compared to those contained in [Table 2-1](#).

Table 2-1: Simulation results from ADDPLAN MC (x100,000 simulations per scenario) with a capped maximum sample size of 80 per arm using a Bonferroni intersection test

Scenario	Treatment Effect		Standard Deviation	Power	Interim			Average Sample Size
	Dose 1	Dose 2			Proportion Futility	Proportion Selecting Low Dose	Proportion Selecting High Dose	
1	0.0	0.0	3.5	0.020	0.335	0.474	0.474	169.0
2	1.0	1.0		0.400	0.049	0.781	0.782	203.3
3	1.0	1.5		0.632	0.023	0.657	0.914	199.1
4	1.5	1.5		0.750	0.011	0.838	0.841	199.8
5	1.0	2.0		0.864	0.008	0.474	0.975	186.4
6	1.5	2.0		0.892	0.004	0.697	0.942	191.7
7	2.0	2.0		0.943	0.002	0.859	0.860	189.9
8	0.0	0.0	4.0	0.020	0.335	0.467	0.463	168.1
9	1.0	1.0		0.315	0.066	0.734	0.733	199.9
10	1.0	1.5		0.515	0.037	0.621	0.875	198.2
11	1.5	1.5		0.632	0.021	0.795	0.797	199.4
12	1.0	2.0		0.755	0.016	0.468	0.953	189.5
13	1.5	2.0		0.792	0.010	0.663	0.912	193.7
14	2.0	2.0		0.871	0.005	0.823	0.822	192.3

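### SAP 2.4 states at least 80% power in six scenarios, but its own Table 2-1 gives 75.5% in scenario 12 and 79.2% in scenario 13

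*SAP*

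**What the plan says.** SAP 2.4 describes a two-stage design with 30 participants per arm in Stage 1 and 30 to 50 per arm in Stage 2, and reports its operating characteristics in Table 2-1. The table heading gives the basis as 100,000 simulations per scenario "with a capped maximum sample size of 80 per arm using a Bonferroni intersection test".

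The text above the table says that power in scenarios 5 to 7 and 12 to 14, "when the high dose has an effect compared to placebo of 2 points, are at least 80" percent. It concludes that sample size re-assessment helps "maintain reasonable power when only one dose has a clinically meaningful effect of 2 and the data variability is greater than anticipated", with the SD given as 4. These results are then offered, with others, in support of the stage sizes.

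Three other statements in SAP 2.4 bear on the point:

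- The planning assumption is that "the standard deviation is assumed to be 3.5 to 4".
- Across the scenarios, "the average sample size for the study ranges between 169 and 203 study participants".
- If an overall cap of 240 were used instead of 80 per arm, "then we would expect power for each scenario to be slightly increased compared to those contained in" Table 2-1.

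**The concern.** The sentence and the table disagree. The scenario 12 row gives power, futility, low-dose selection, high-dose selection and average sample size as "0.755 0.016 0.468 0.953 189.5". Its power is therefore 75.5%. Scenario 13 is also below 80%.

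These are also the rows that matter for the sentence's conclusion. A reader who relies on the text would take the type II error, when one dose works and the SD is 4, to be at most 20%. The table gives 24.5% and 20.8%. An SD of 4 lies inside the SAP's own planning range, so this is not a remote case.

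**Working it through.** **Step 1. Read the table.** Power for the six named scenarios, from SAP Table 2-1:

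| Scenario | Effects (dose 1 / dose 2) | SD | Power | Difference from 0.80 |
|---|---|---|---|---|
| 5 | 1.0 / 2.0 | 3.5 | 0.864 | +0.064 |
| 6 | 1.5 / 2.0 | 3.5 | 0.892 | +0.092 |
| 7 | 2.0 / 2.0 | 3.5 | 0.943 | +0.143 |
| 12 | 1.0 / 2.0 | 4.0 | 0.755 | −0.045 |
| 13 | 1.5 / 2.0 | 4.0 | 0.792 | −0.008 |
| 14 | 2.0 / 2.0 | 4.0 | 0.871 | +0.071 |

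The minimum is 0.755. Only scenarios 12 and 13 have one dose at 2 points and an SD of 4. Scenario 14 has both doses at 2, and scenarios 5 to 7 use an SD of 3.5. Type II errors are 1 − 0.755 = 0.245 and 1 − 0.792 = 0.208.

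**Step 2. Rule out simulation noise.** The Monte Carlo standard error is √(p(1 − p)/100,000).

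- Scenario 12: √(0.755 × 0.245/100,000) = 0.00136. The 95% range is 75.2% to 75.8%.
- Scenario 13: √(0.792 × 0.208/100,000) = 0.00128. The 95% range is 78.9% to 79.5%.

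Neither range reaches 80%.

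**Step 3. Check that the table, not the sentence, is right.** I simulated the design with 200,000 runs per scenario and these inputs:

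- 30 per arm in Stage 1 (SAP 2.4).
- A dose dropped if its one-sided p exceeds 0.5; the best dose kept, plus the other if within 1 point (SAP 4.4.1).
- Stage 2 size per arm from the SAP 2.4 formula, 2 × SD² × [Φ⁻¹(0.9) + Φ⁻¹(1 − CRP)]²/Δ², using the observed Stage 1 effect and bounded to 30–50.
- Equal-weight inverse-normal combination and closed testing with a Bonferroni intersection test, at one-sided 0.025 (SAP 8.2.2 and Protocol 9.4.1).
- Power taken as rejection for at least one dose.

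SAP 2.4 halves the conditional error when two doses go forward. I ran it with and without halving.

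| Scenario | Table 2-1 | Halved | Not halved |
|---|---|---|---|
| 5 | 0.864 | 0.866 | 0.861 |
| 6 | 0.892 | 0.894 | 0.888 |
| 7 | 0.943 | 0.946 | 0.941 |
| 12 | 0.755 | 0.758 | 0.753 |
| 13 | 0.792 | 0.797 | 0.790 |
| 14 | 0.871 | 0.875 | 0.868 |

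All 14 scenarios in Table 2-1 reproduce closely, including the null scenarios (0.020 and 0.019 against 0.020). With halving, the average sample size is 189.6 in scenario 12 (table 189.5) and 194.4 in scenario 13 (table 193.7). A separate run of 400,000 per scenario gave 0.759 and 0.797 for scenarios 12 and 13. The table is sound.

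**Step 4. Try the alternative cap.** With 150 participants in Stage 2 whatever the number of doses, I assumed at most 150/2 = 75 per arm if one dose is selected and 150/3 = 50 if two are. Over the same variants, scenario 12 gives 0.778 to 0.785 and scenario 13 gives 0.806 to 0.813. Scenario 12 stays below 80%.

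**Step 5. The two side points.** An SD of 4 is the upper end of the assumed 3.5 to 4, so it is not beyond what was anticipated. The smallest average sample size in Table 2-1 is 168.1 (scenario 8), not 169; scenario 1 is 169.0. The upper figure of 203 agrees with scenario 2 (203.3).

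**The case against.** The strongest reply concerns weight. No test, alpha level, cap or stopping rule uses this sentence, and the correct figures stand in the table directly below it. The actual Stage 2 size comes from the conditional-power formula. The conclusion that power stays reasonable is qualitative, and 75.5% weakens it without plainly refuting it. Support for the stage sizes also rests on the futility risk of under 3%, which the table confirms: 0.016, 0.010 and 0.005 in scenarios 12 to 14. All of this stands. It makes the point a wrong stated figure and not a design defect, but it does not make the figure right.

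Scenario 13 is fairly called marginal. It is 0.8 points short, and a simulation that differs from the sponsor's software by up to half a point cannot settle which side of 80% it lies on. That row rests on the printed value alone, and scenario 12 carries the finding.

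The results under the 240 cap vary with implementation by more than Monte Carlo error, and the 75-per-arm maximum is an assumption. They should be read as about 78% and about 81%. The remark on that cap is in any case conditional and promises only a slight gain, whereas the disputed sentence reports the 80-per-arm results.

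The SD phrase could be read as meaning above the lower planning value, and 169 against 168.1 is less than one participant, in a null scenario. Both are minor, and the finding does not depend on them.

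**Conclusion.** The concern holds. The claim of at least 80% power is wrong for two of the six scenarios it names, and these are the two that match its conclusion. The shortfall is 4.5 points in scenario 12 and a marginal 0.8 points in scenario 13. The contradiction rests only on the SAP's printed text and table. The simulation adds that the table is the reliable side, and that the larger overall cap would bring scenario 13 to about 81% but leave scenario 12 at about 78%.

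This should be corrected, because the SAP offers the sentence in support of its stage sizes. It does not call for a change to the design. The scenario numbers, power and SD in the matching text of Protocol 9.9 are redacted in the public copy, so no error in the protocol is claimed.

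**What to change.** In SAP 2.4, replace the power statement with the table's figures, for example:

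> Power is 86.4% to 94.3% in scenarios 5 to 7 and 75.5% to 87.1% in scenarios 12 to 14. With a 2-point effect in one dose only and an SD of 4, power is 75.5% to 79.2% under the cap of 80 per arm.

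In the same edit, describe an SD of 4 as the upper end of the assumed range, and change the lower average sample size from 169 to 168. The sponsor should check the unredacted Protocol 9.9 and correct it only if it makes the same statement.

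The cost is a text correction in one SAP section, and a slightly less favourable stated power. Enrolment, alpha and the analysis stay as they are.
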